#### Abbreviated Item Content for the SF-36v2® Health Survey Health Domain Scales

Scale	Item	Abbreviated Item Content
Physical Functioning (PF)	3a	Vigorous activities, such as running, lifting heavy objects, or participating in strenuous sports
	3b	Moderate activities, such as moving a table, pushing a vacuum cleaner, bowling, or playing golf
	3c	Lifting or carrying groceries
	3d	Climbing several flights of stairs
	3e	Climbing one flight of stairs
	3f	Bending, kneeling, or stooping
	3g	Walking more than a mile
	3h	Walking several hundred yards

	3i	Walking one hundred yards
	3j	Bathing or dressing oneself
Role-Physical (RP)	4a	Cut down the amount of time one spent on work or other activities
	4b	Accomplished less than you would like
	4c	Limited in kind of work or other activities
	4d	Had difficulty performing work or other activities (e.g., it took extra effort)
Bodily Pain (BP)	7	Intensity of bodily pain
	8	Extent pain interfered with normal work
General Health (GH)	1	Is your health: excellent, very good, good, fair, poor
	11a	Seem to get sick a little easier than other people
	11b	As healthy as anybody I know
	11c	Expect my health to get worse
	11d	Health is excellent
Vitality (VT)	9a	Feel full of life
	9e	Have a lot of energy
	9g	Feel worn out
	9i	Feel tired
Social Functioning (SF)	6	Extent health problems interfered with normal social activities
	10	Frequency health problems interfered with social activities
Role-Emotional (RE)	5a	Cut down the amount of time spent on work or other activities
	5b	Accomplished less than you would like
	5c	Did work or other activities less carefully than usual
Mental Health (MH)	9b	Been very nervous
	9c	Felt so down in the dumps that nothing could cheer you up
	9d	Felt calm and peaceful
	9f	Felt downhearted and depressed
	9h	Been happy
Reported Health Transition (HT)	2	How health is now compared to 1 year ago
An excerpt from the User's Manual for the SF-36v2 Health Survey		

**Appendix 2.3 Functional Assessment of Chronic Illness Therapy-Fatigue (FACIT-F)**

For any FACIT measure, items are scored on a 0 – 4 response scale with anchors ranging from “Not at all” to “Very much so”. To score the FACIT-F, scores are calculated by first reversing negatively stated-items (subtracting the response from ‘4’) and then summing the reverse scores. A total score is then derived by summing all scores.

In cases where individual items are missing, subscale scores can be prorated using the average of the other answers in the scale. This is acceptable as long as more than 50% of the items were answered in the subscale (e.g., a minimum of 7 of 13 items.).

**Appendix 2.4 Disease Activity Score in 28 joints-C-reactive protein (DAS28-CRP)**

The DAS28-CRP considers 28 tender and swollen joint counts, general health (subject's global assessment of disease activity (SGADA) using a 100 mm visual analogue scale (VAS) with 0=best, 100=worst), plus levels of an acute phase reactant (CRP (mg/L)).

DAS28 values were calculated as follows:

$$\text{DAS28-CRP} = 0.56 * \sqrt{(\text{TJC28})} + 0.28 * \sqrt{(\text{SJC28})} + 0.014 * \text{SGADA} + 0.36 * \ln(\text{CRP}+1) + 0.96;$$

where TJC=tender joint count and SJC=swollen joint count;

SGADA = subject's global assessment of disease activity on a 0-100 VAS.

If one or more components are missing in the formula, then DAS28-CRP is set to be missing.

**Appendix 2.5 Disease Activity index for Psoriatic Arthritis (DAPSA)**

DAPSA is the numerical sum of 66 swollen and 68 tender joint counts, pain, SGADA (pain and SGADA scored on a 0–10 scale) and CRP (mg/dL))

DAPSA = TJC68 + SJC66 + SGADA/10 + SAPVAS/10 + CRP;

where TJC=tender joint count and SJC=swollen joint count;

ln = natural logarithm;

SGADA = subject's global assessment of disease activity on a 0-100 VAS;

SAPVAS = subject's global assessment of pain on a 0-100 VAS;

CRP = C-reactive protein measured in mg/dL.

The cDAPSA, which was derived from the DAPSA, includes all DAPSA components but excludes CRP to obtain a fully clinical score.

A DAPSA, cDAPSA score of  $\leq 14$  represents low disease activity, and a score of  $\leq 4$  represents remission.

**Appendix 2.6 Psoriatic Arthritis Disease Activity Score (PASDAS)**

The PASDAS is calculated using the following formula:

$$\text{PASDAS} = (0.18\sqrt{\text{IGADA}}) + (0.159\sqrt{\text{SGADA}}) - (0.253\sqrt{\text{SF-36PCS}}) + (0.101 * \ln(\text{SJC66}+1)) + (0.048 * \ln(\text{TJC68}+1)) + (0.23 * \ln(\text{LEI}+1)) + (0.37 * \ln(\text{LDI}+1)) + (0.102 * \ln((\text{CRP} * 10) + 1) + 2) * 1.5$$

where swollen and tender joint counts can range from 0 to 66 and 68 joints, respectively; and CRP = C-reactive protein measured in mg/L. The PASDAS score ranges from 0-10 with higher scores indicating worse disease activity.

where TJC=tender joint count and SJC=swollen joint count;

ln = natural logarithm; all VAS scores are from 0-100mm;

IGADA = investigator's global assessment of disease activity;

SGADA = subject's global assessment of disease activity;

PCS = physical component summary scale of the SF-36;

LEI = Leeds enthesitis index;

LDI = Leeds dactylitis index;

CRP = C-reactive protein measured in mg/dL.

The score range of the PASDAS is 0 to 10, with worse disease activity represented by higher scores.

**Appendix 2.7 Psoriatic Arthritis Impact of Disease Scoring and Calculation Rules  
(PsAID)**

The PsAID is calculated based on 9 Numerical rating scales (NRS) questions. Each NRS is assessed as a number between 0 and 10.

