8.1.1.4. Psoriatic Arthritis Disease Activity Score

The Psoriatic Disease Activity Score (PASDAS) is a weighted index comprising the following assessments:

- 68 tender joint count (see [Section 8.1.3.1](#))
- 66 swollen joint count (see [Section 8.1.3.1](#))
- Subject's Global Assessment of Disease Activity (see [Section 8.1.2.2](#))
- Investigator's Global Assessment of Disease Activity (see [Section 8.1.3.2](#))
- 36-Item Short Form Survey (SF-36; see [Section 8.1.2.8](#))
- Leeds Enthesitis Index (see [Section 8.1.3.5](#))
- Leeds Dactylitis Index (see [Section 8.1.3.6](#))
- CRP level in mg/dL.

The score range of the PASDAS is 0 to 10, with worse disease activity represented by higher scores. Change in PASDAS index will be evaluated at Week 16.

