**Table 1 Laboratory Tests**

Hematology Test (SI unit)	Serum Chemistry Test (SI unit)	Urinalysis

 
• Red Blood Cell Count (<math>10^{12}/L</math>)
 
• Hemoglobin (g/L)
 
• Hematocrit (%)
 
• White Blood Cell Count (<math>10^9/L</math>)
 
• Differential WBC (<math>10^9/L</math> and %) 
 
◦ Neutrophils
 
◦ Lymphocytes
 
◦ Eosinophils
 
◦ Basophils
 
◦ Monocytes
 
 
 
• Platelet count (<math>10^9/L</math>)
 
• RBC indices: 
 
◦ Mean corpuscular volume (MCV) (fl)
 
◦ Mean corpuscular hemoglobin (MCH) (Pg)
 
◦ %Reticulocytes
 
 
 
	
 
• Alanine aminotransferase (ALT) (U/L)/Serum glutamic-pyruvic transaminase
 
• Aspartate aminotransferase (AST) (U/L)/Serum glutamic-oxaloacetic transaminase
 
• Total and direct Bilirubin (mmol/L)
 
• Alkaline phosphatase (U/L)
 
• Total protein (g/L)
 
• Glucose (not fasting) (mmol/L)
 
• Creatinine (mmol/L)
 
• Blood Urea Nitrogen (mmol/L)
 
• Calcium (mmol/L)
 
• Potassium (mmol/L)
 
• Sodium (mmol/L)
 
• C-reactive protein (mg/L)
 
• A1C (%)
 
• High-density-lipoprotein (HDL) (mmol/L)
 
• International normalized ratio*
 
• Total cholesterol (mmol/L)
 
	
 
• Specific gravity
 
 
Urinalysis (dipstick)
 
 
• pH
 
• Glucose
 
• Proteins
 
• Red Blood Cell Count
 
• White Blood Cell Count
 
• Ketones
 
 
Microscopic examination (if blood or protein is abnormal)

Pregnancy Testing	Other Screening Tests	Other Tests

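### The PASDAS formula in SAP Appendix 2.6 applies the factor 1.5 only to the CRP term and the constant, so the score cannot reach its stated floor of 0; separately, CRP is given in two units

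*SAP*

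**What the plan says.** SAP Appendix 2.6 builds PASDAS from eight weighted terms and a constant. The expression ends "0.102 * \ln((\text{CRP} * 10) + 1) + 2) * 1.5". With the opening bracket that stands before 0.102, the last bracket pair encloses the CRP term and the 2, and nothing else. The brackets balance over the whole expression (14 opening, 14 closing), so it can be programmed as it stands.

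The range is given twice in the appendix, the second time as "The score range of the PASDAS is 0 to 10, with worse disease activity represented by higher scores". Protocol 8.1.1.4 gives the same range and lists the components, but prints no formula.

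On CRP, the appendix first says "CRP = C-reactive protein measured in mg/L. The PASDAS score ranges from 0-10 with higher scores indicating worse disease activity" and a few lines later "CRP = C-reactive protein measured in mg/dL". Protocol 8.1.1.4 has "CRP level in mg/dL". SAP Table 1 lists the laboratory value as "C-reactive protein (mg/L)", while SAP 6.4.2 summarises baseline CRP in mg/dL.

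Change in PASDAS at Weeks 16, 24 and 52 is an exploratory endpoint (SAP 2.6 and 6.6.5). Baseline PASDAS is also summarised (SAP 6.4.2).

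**The concern.** A scale factor placed at the end of a weighted sum would normally apply to the whole sum. Here it applies to one of the eight terms and the constant. If that is a misplaced bracket, a programmer who follows the appendix literally produces a PASDAS on a compressed scale, with CRP weighted more heavily against the other components than intended. Baseline values and changes would then not be comparable with PASDAS computed elsewhere. The appendix's own range offers a test of the bracket that needs no outside source.

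The two CRP units raise a different question: which value goes into a formula that already multiplies CRP by 10.

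**Working it through.** **Two forms compared.** Let A be the sum of the seven non-CRP terms and C = 0.102·ln(10·CRP + 1).
- As printed: A + 1.5·(C + 2).
- Whole sum scaled: 1.5·(A + C + 2). Neither document prints this form.

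**Input ranges.** For IGADA and SGADA, "all VAS scores are from 0-100mm". Joint counts run to 66 and 68 (Appendix 2.6) and LEI to 6 (Protocol 8.1.3.5). SAP Appendix 2.2 makes the version 1 PCS a mean of 0–100 subscales, so at most 100; it gives no range for version 2, and 0–100 is assumed. No upper limit is given for LDI or CRP.

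**Can the stated floor of 0 be reached?** Set every input except PCS to zero. The printed form becomes 3 − 0.253·√PCS and the whole-sum form 1.5·(2 − 0.253·√PCS).

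| PCS | As printed | Whole sum × 1.5 |
|---|---|---|
| 50 | 1.21 | 0.32 |
| 57 | 1.09 | 0.13 |
| 60 | 1.04 | 0.06 |
| 100 | 0.47 | −0.80 |

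The printed form equals 0 only at PCS = (3/0.253)² = 140.6. The whole-sum form equals 0 at (2/0.253)² = 62.5. CRP is zero here, so its unit plays no part.

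**Top of the range.** With both VAS scores, both joint counts and LEI at their maxima, PCS 20, LDI 20 and CRP 10 mg/dL, the printed form gives 8.17 and the whole-sum form 10.40. At PCS 0, LDI 100 and CRP 30 mg/dL they give 10.05 and 13.13.

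**Change in one illustrative subject (assumed inputs).** Order: IGADA, SGADA, PCS, SJC, TJC, LEI, LDI, CRP in mg/dL.
- Baseline 60, 60, 35, 10, 18, 2, 5, 1.0: A = 2.428, C = 0.245.
- Week 16 20, 25, 45, 3, 6, 0, 0, 0.4: A = 0.136, C = 0.164.

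| | Baseline | Week 16 | Change |
|---|---|---|---|
| As printed | 5.80 | 3.38 | −2.41 |
| Whole sum × 1.5 | 7.01 | 3.45 | −3.56 |

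The ratio is 2.41/3.56 = 0.68, so the printed change is about 32% smaller. The constant cancels in a change score. What remains is that each non-CRP term counts 1/1.5 = two thirds as much, while the CRP term is the same in both forms (0.102 × 1.5 = 0.153).

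**CRP unit.** Entering mg/L where the formula expects mg/dL adds 0.153·[ln(100c + 1) − ln(10c + 1)] at c mg/dL, in either form. At c = 1 this is 0.153·(ln 101 − ln 11) = 0.34, and it never exceeds 0.153·ln 10 = 0.35. The illustrative printed change moves only from −2.41 to −2.43. The factor 10 turns mg/dL into mg/L inside the logarithm, which fits an mg/dL input and agrees with Protocol 8.1.1.4.

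**The case against.** The strongest reply is that the range does not by itself prove where the bracket belongs. The whole-sum form also leaves 0–10: −0.80 at PCS 100, 10.40 in the severe case above, and further at joint extremes. Neither document prints that form, and the cited source (SAP reference 14) was not available for this review. This stands. The range shows that the printed expression disagrees with the appendix's own description. The whole-sum form is favoured because its floor lies near 0 at plausible PCS values, but the source has to confirm it.

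The formula was also read from a PDF by program, and an outer bracket pair could have been lost. The balanced count makes that unlikely without excluding it.

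On impact, multiplying an entire score by 1.5 leaves a test statistic unchanged. The printed form departs from that only through the heavier relative weight of CRP, which supplies 1.5 × (0.245 − 0.164) = 0.12 of the 2.41 change in the example. So the size of reported values and changes is affected far more than any comparison between arms.

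A reader might also infer that the two CRP units help to cause the range failure or the smaller change. They do neither: the floor is the same in both units, and mg/L makes the example change slightly larger. Nor is a score of 10 strictly barred, because LDI and CRP have no stated cap.

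**Conclusion.** The point holds in a limited form. As printed, PASDAS cannot reach the floor of 0 that the SAP and the protocol both state; its minimum is 0.47 at PCS 100 and about 1.1 at PCS 57. This rests only on the printed bracket and a PCS of at most 100. The 32% smaller change depends on two assumptions: that the whole-sum form is the intended one, and the illustrative inputs. The CRP unit conflict is a separate ambiguity worth about 0.34 points on a score at 1 mg/dL and almost nothing on change.

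The effect is confined to the baseline PASDAS summary and the exploratory PASDAS values and changes at Weeks 16, 24 and 52. SAP 6.6.5 treats exploratory p-values as descriptive and plans none after Week 16. It would be wrong to infer that a trial conclusion is at risk: PASDAS is outside the test sequence in SAP 6.6, and no PASDAS cut-off or responder definition is planned.

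**What to change.** Check the bracket against the PASDAS source cited in the SAP (reference 14). Subject to that check, print the formula so that 1.5 multiplies the entire sum including the 2, and note that computed values can fall slightly outside 0–10 at extremes.

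State CRP once, in mg/dL as in Protocol 8.1.1.4, delete the mg/L line, and add the conversion from the laboratory unit in SAP Table 1 (mg/L divided by 10).

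The cost is an edit to one SAP appendix and a check of the derivation program. Design, data collection and the testing sequence do not change. If PASDAS has already been programmed from the printed formula, the derivation and its tables need to be rerun.

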**1. Calculation**

PsAID final value = (PsAID1 (pain) NRS value (range 0-10) x 0.174) + (PsAID2 (fatigue) NRS value (range 0-10) x 0.131) + (PsAID3 (skin) NRS value (range 0-10) x 0.121) + (PsAID4 (Work and/or leisure activities) NRS value (range 0-10) x 0.110) + (PsAID5 (function) NRS value (range 0-10) x 0.107) + (PsAID6 (discomfort) NRS value (range 0-10) x 0.098) + (PsAID7 (sleep) NRS value (range 0-10) x 0.089) + (PsAID8 (coping) NRS value (range 0-10) x 0.087) + (PsAID9 (anxiety) NRS value (range 0-10) x 0.085)

Thus, the range of the final PsAID value is 0-10 where higher figures indicate worse status.

**2. Missing data imputation**

If one of the 9 NRS values composing the PsAID is missing, the imputation is as follows:

- a. calculate the mean value of the 8 other (non-missing) NRS (range, 0-10)
- b. impute this value for the missing NRS
- c. Then, calculate the PsAID as explained above.

If 2 or more of the NRS are missing, the PsAID is considered as missing value (no imputation).

**Appendix 2.8 Psoriasis Area and Severity Index and Affected Body Surface Area (PASI)**

Psoriasis Area and Severity Index is an index used to express the severity of psoriasis.

### 1. Intensity

A representative area of psoriasis is selected for each body region. The intensity of redness/erythema, thickness, and scaling of the psoriasis is assessed as absent/none (0), mild (1), moderate (2), severe (3), or very severe (4).

### 2. Calculation for intensity

The three intensity scores are added up for each of the four body regions to give subtotals A1, A2, A3, A4.

Each subtotal is multiplied by the body surface area represented by that region.

- A1 x 0.1 gives B1
- A2 x 0.2 gives B2
- A3 x 0.3 gives B3
- A4 x 0.4 gives B4

### 3. Area

The percentage area affected by psoriasis is evaluated in the four regions of the body. In each region, the area is expressed as nil (0), 1-9% (score 1), 10-29% (score 2), 30-49% (score 3), 50-69% (score 4), 70-89% (score 5) or 90-100% (score 6).

- Head and neck
- Upper limbs
- Trunk
- Lower limbs

### 4. Calculations for area

Each of the body area scores is multiplied by the area affected.

- B1 x (0 to 6)= C1
- B2 x (0 to 6)= C2
- B3 x (0 to 6)= C3
- B4 x (0 to 6)= C4

### 5. Total score

The PASI score is C1 + C2 + C3 + C4.

**Appendix 2.9 modified Nail Psoriasis Severity Index (mNAPSI)**

mNAPSI is a scale used to evaluate the severity of nail bed psoriasis and nail matrix psoriasis by area of involvement in the nail unit.

NAPSI is used to assign a score to each nail for nail bed and nail matrix psoriasis: Nail plate is assessed for nail matrix psoriasis by the presence of any feature of nail matrix psoriasis, including nail pitting, leukonychia, red spots in the lunula, and crumbling in each quadrant of the nail. Nail bed psoriasis is assessed by the presence of any features of nail bed psoriasis, including onycholysis, oil drop (salmon patch) dyschromia, splinter hemorrhages, and nail bed hyperkeratosis in each quadrant of the nail.

The score is 0 if the findings are not present, 1 if they are present in 1 quadrant of the nail, 2 if present in 2 quadrants of a nail, 3 if present in 3 quadrants of a nail, and 4 if present in 4 quadrants of a nail. Thus, each nail has a matrix score (0-4) and a nail bed score (0-4), and the total nail score is the sum of those 2 individual scores (0-8). Sum of the total score of all involved fingernails is the total mNAPSI score.

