8.1.3.4. Modified Nail Psoriasis Severity Index

The Nail Psoriasis Severity Index is a numeric, reproducible, objective, simple tool for evaluation of nail psoriasis ([Rich and Scher, 2003](#)). Nail bed psoriasis includes onycholysis, splinter hemorrhages, hyperkeratosis, and "oil-drop change", while nail matrix psoriasis includes pitting, leukonychia, lunular red spots, and nail plate crumbling ([Mease, 2011](#)).

A modification of this system, the modified Nail Psoriasis Severity Index (mNAPSI), is a shorter and more feasible scoring system that has demonstrated excellent interrater reliability and has been used in PsA clinical trials ([Mease, 2011; Cassell et al, 2007](#)). For each fingernail, 7 groups of features are evaluated: pitting, onycholysis and oil-drop dyschromia, nail plate crumbling,

leukonychia, splinter hemorrhages, hyperkeratosis, and red spots in the lunula. Pitting, onycholysis and oil-drop dyschromia, and crumbling (including fragmentation and horizontal ridging of the nail bed) are graded from 0 to 3 in severity. Leukonychia, splinter hemorrhages, hyperkeratosis, and red spots in the lunula are graded as either present or absent.

An mNAPSI will be calculated at the designated study visits listed in the SoA ([Section 1.3](#)).

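### SAP Appendix 2.9 scores mNAPSI by a NAPSI quadrant count that does not fit the seven-feature assessment in protocol 8.1.3.4, and Appendix 2.6 gives PASDAS CRP in two units (minor; exploratory endpoints only)

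*SAP*

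**What the plan says.** **Protocol 8.1.3.4** presents mNAPSI as a shorter modification of NAPSI and describes the assessment: "For each fingernail, 7 groups of features are evaluated". Three groups carry a severity grade (pitting; onycholysis with oil-drop change; crumbling). The text reads "crumbling (including fragmentation and horizontal ridging of the nail bed) are graded from 0 to 3 in severity". The other four are binary: red lunular spots, leukonychia, splinter hemorrhages and hyperkeratosis ("hyperkeratosis, and red spots in the lunula are graded as either present or absent"). The section then states "An mNAPSI will be calculated at the designated study visits listed in the SoA". It mentions no quadrants and gives no rule for combining the seven items.

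**SAP Appendix 2.9** carries the mNAPSI heading, but its scoring text says "NAPSI is used to assign a score to each nail for nail bed and nail matrix psoriasis". A quadrant counts toward the matrix score "by the presence of any feature of nail matrix psoriasis", and the bed score works the same way. The rule is "The score is 0 if the findings are not present, 1 if they are present in 1 quadrant of the nail", continuing to 4 for all four quadrants. Matrix and bed scores are added to give 0 to 8 per nail, and "Sum of the total score of all involved fingernails is the total mNAPSI score". The appendix cites no source, and the SAP reference list has none for nail scoring.

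**SAP Appendix 2.6** gives the PASDAS formula with a term in the log of ten times CRP plus one. It states the CRP unit twice, once as mg/L and once as mg/dL.

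SAP 2.6 lists change in mNAPSI (subjects above zero at baseline) and change in PASDAS as exploratory. SAP 6.6.5 treats exploratory p-values as descriptive.

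**The concern.** The SAP applies the scoring of one index to the name of another. Severity grades and present/absent flags do not say how many quadrants of a nail are involved, so a programmer holding data of the kind the protocol describes has no input for the SAP rule. If quadrants were collected instead, the score reported as mNAPSI would not be the one the protocol describes, and it would not respond to a change in severity grade.

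The outputs at stake are the baseline mNAPSI summary (SAP 6.4.2), the repeated-measures comparison at Week 16 and the descriptive summaries at Weeks 24 and 52 (SAP 6.6.5).

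The CRP slip is separate and smaller. Laboratory CRP is in mg/L in SAP Table 1, and DAS28-CRP uses mg/L (Appendix 2.4), whereas DAPSA uses mg/dL (Appendix 2.5). A programmer could plausibly enter the wrong unit in PASDAS.

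**Working it through.** **1. Nail score.** The SAP's own figure reproduces: matrix 0–4 plus bed 0–4 gives 4 + 4 = 8 per nail, or 8 × 10 = 80 over ten fingernails.

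| | Protocol 8.1.3.4 | SAP Appendix 2.9 |
|---|---|---|
| Recorded per nail | 7 feature groups | quadrants with any matrix feature; quadrants with any bed feature |
| Scale | 3 graded 0–3, 4 present/absent | 0–4 plus 0–4 |
| Severity used | yes, for three groups | no |
| Total | no rule stated | sum over involved fingernails |

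Neither record determines the other, so this is not a rescaling. Adding the protocol's grades would give 3 × 3 + 4 × 1 = 13 per nail, but that sum is an assumption and the protocol does not state it. Comparing 8 with 13 therefore measures nothing about the endpoint.

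One constructed nail shows that the two descriptions can disagree. Suppose pitting falls from grade 3 to grade 1 and leukonychia clears, with some pits left in all four quadrants. The SAP matrix score is 4 before and 4 after (change 0), although two protocol features improved. The example shows the direction of the problem, not its size.

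**2. PASDAS CRP.** In the printed formula CRP contributes 0.102 × 1.5 × ln(10x + 1) = 0.153 × ln(10x + 1), where x is the value entered. Let c be CRP in mg/dL; the same CRP in mg/L is 10c. The values of c are assumed illustrations.

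| c (mg/dL) | enter c | enter 10c | shift in level |
|---|---|---|---|
| 0.1 | 0.106 | 0.367 | 0.261 |
| 0.4 | 0.246 | 0.568 | 0.322 |
| 1.0 | 0.367 | 0.706 | 0.339 |
| 5.0 | 0.602 | 0.951 | 0.350 |

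The shift cannot exceed 0.153 × ln(10) = 0.352.

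The endpoint is change. With one unit used at both visits, the CRP contribution to change is:

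| CRP change (mg/dL) | mg/dL entered | mg/L entered | difference |
|---|---|---|---|
| 1.0 to 0.4 | −0.121 | −0.138 | 0.017 |
| 1.0 to 0.1 | −0.261 | −0.339 | 0.078 |
| 5.0 to 0.1 | −0.496 | −0.584 | 0.088 |

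**3. Which unit is intended.** Protocol 8.1.1.4 gives mg/dL for PASDAS. The SAP's DAPSA appendix and baseline table use mg/dL. The formula's factor of ten is itself the conversion from mg/dL to mg/L. The mg/L line in Appendix 2.6 is the odd one out.

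**The case against.** The strongest reply is that little depends on this. Change in mNAPSI is one of dozens of exploratory variables, is restricted to a subset, has descriptive p-values and gets no p-value after Week 16. That stands, and it is why the point is minor.

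The second reply is that the harm rests on a document nobody outside the sponsor can see. That also stands. A reader might infer that the mNAPSI endpoint cannot be computed at all. The documents do not support this: the SAP names eCRF version 2.1 as a source but does not show its nail fields, and they may hold quadrants. What the documents do support is that the protocol and the SAP disagree about how nails are scored.

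A reader might also infer that the analysis subset (mNAPSI above zero at baseline) changes with the rule, or that it certainly does not. Neither is established. The feature lists largely agree, so the subset is probably similar. They are not identical, though: the protocol counts fragmentation and ridging under crumbling, and the SAP does not mention them.

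On CRP, it is fair to say that the surrounding text already points to mg/dL. SAP 6.1 allows results to arrive in SI units, conventional units or both, and it refers laboratory units to the table shells, which are not shown. A conversion may be given there. The two contradictory unit statements in Appendix 2.6 still need correcting.

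**Conclusion.** The plan is wrong as written on a minor point. The score defined in Appendix 2.9 cannot be derived from an assessment made as protocol 8.1.3.4 describes it, and a quadrant count discards the severity grades. Confidence is high for the mismatch between the texts. Whether the derivation would fail in practice is unknown without the eCRF, and no size of effect on change in mNAPSI can be stated without a summation rule in the protocol.

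For PASDAS, using mg/L in error would raise a single score by about 0.26 to 0.35, on a scale the SAP gives as 0 to 10. Change would move by about 0.02 to 0.09, assuming CRP values between 0.1 and 5 mg/dL and one unit throughout.

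It would be wrong to carry either item over to the main results. Neither score enters the alpha-controlled testing sequence, so the primary and secondary endpoints, type I error control and power are unaffected.

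**What to change.** 1. Look at the nail fields in eCRF version 2.1 before programming.
   - **If they hold the seven features:** replace the text of Appendix 2.9 with the mNAPSI scoring rule from the validation study that protocol 8.1.3.4 cites. Do not assume a simple sum.
   - **If they hold quadrants:** keep the SAP rule but call the score NAPSI in the SAP and its outputs, and correct the protocol description at the next amendment.
2. In Appendix 2.6, delete the mg/L statement and define CRP once in mg/dL. State that mg/dL equals mg/L divided by 10, unless the table shells already say so.

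**Cost.** In the seven-feature case: two appendix edits, the matching derivation code, and a look at the eCRF and the cited source. In the quadrant case, add renaming the score in the SAP and its outputs and a protocol amendment, which needs IRB/IEC approval under protocol 10.1.1. Data collection does not change in either case.
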